6.10.1.4. Treatment of Overdose

Study drug overdose will be summarized only if it occurs in $\geq 1\%$ of patients. Otherwise, only a data listing will be generated, including treatment overdose AE reported data.

6.10.2. Electrocardiograms

Changes from baseline in heart rate (HR), PR interval, and QT corrected for HR using Fridericia's corrected QT interval (QTcF) will be analyzed using the MMRM described in Section 6.1.

The threshold analyses will only include HR, PR interval, and QTcF, by visit and treatment. The thresholds are defined in [Table GBGL.3](#).

Table GBGL.3. Abnormality Criteria for Heart Rate, PR Interval, and QTcF

Parameter (Unit)	Visit	Threshold Definition
HR (bpm)	Baseline (Visit 1)	>100, ≥ 130
	Postbaseline	>100 and CFB >15
PR interval (msec)	Baseline (Visit 1)	≥ 220
	Postbaseline	≥ 220
		≥ 220 and (%CFB >0 and $\leq 25\%$)
		≥ 220 and (%CFB >25%)
QTcF (msec)	Baseline (Visit 1)	>450 (Male) or >470 (Female)
		>480
		>500
	Postbaseline	>450 (Male) or >470 (Female)
		>480
		>500
		>30 CFB
		>60 CFB

Abbreviations: %CFB = percent change from baseline; CFB = change from baseline; HR = heart rate; QTcF = Fridericia's corrected QT interval.

The qualitative summary related to treatment-emergent cardiac conduction and rhythm abnormalities will be reported by treatment.

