10.3.4.7. Electrocardiograms

Descriptive statistics for the absolute measurements, changes from baseline, and clinically relevant changes for selected ECG parameters defined in the SAP, including QT corrected for heart rate (HR) using Fridericia's formula (QTcF), will be presented by treatment and visit. These parameters will be analyzed using a similar MMRM as that described in Section 10.3.1 for continuous variable analyses.

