Table GBGL.1 shows the objectives and endpoints of the study.

Table GBGL.1. Objectives and Endpoints

Objectives	Endpoints

Primary To demonstrate that once weekly dulaglutide 4.5 mg and/or 3.0 mg is superior to dulaglutide 1.5 mg as measured by change from baseline in HbA1c at 36 weeks in patients with inadequately controlled T2D on concomitant metformin therapy.
	
 • The change in HbA1c from baseline

Secondary Efficacy: To demonstrate that once weekly dulaglutide 4.5 mg and/or 3.0 mg is superior to dulaglutide 1.5 mg for secondary efficacy parameters at 36 weeks (controlled for Type 1 error).
 
Safety: To compare each investigational dulaglutide arm (4.5 mg, 3.0 mg) to the 1.5 mg arm for selected safety parameters through 36 and 52 weeks (unless noted otherwise).
 
Pharmacokinetics (PK) and Pharmacodynamics (PD): To characterize dulaglutide PK and the dose and/or exposure-response relationships for key efficacy (eg, HbA1c and weight), and safety (eg, heart rate [HR]) endpoints.
	
 • The change in body weight from baseline • Proportion of patients achieving HbA1c target <7.0% (53 mmol/mol) • The change in fasting serum glucose (FSG) from baseline • Incidence of treatment-emergent adverse events (TEAEs) and discontinuation of study drug due to adverse events (AEs) • Adjudicated and confirmed cardiovascular and pancreatic AEs • Incidence of thyroid neoplasm AEs • Incidence of treatment-emergent (TE) dulaglutide anti-drug antibodies (ADA) and systemic hypersensitivity reactions • Changes from baseline in pulse rate • Electrocardiogram (ECG) parameters • Occurrence of hypoglycemic episodes • PK parameters (eg, maximum concentration [C_{max}], area under the curve [AUC]) at steady state • PD evaluations may include changes from baseline in HbA1c, body weight, and HR at Weeks 36 and 52

Objectives	Endpoints

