The treatment-regimen estimand is included as primary at the request of the US Food and Drug Administration (FDA). The efficacy estimand will be considered primary for all other purposes, and will be applied to all efficacy outcomes unless otherwise specified to demonstrate the effect of treatment and avoid confounding effects with other antihyperglycemic agents.

Each of the estimands will be tested at the full significance level of 0.05.

Analyses of safety parameters will be conducted for the Safety Population unless otherwise specified.

Countries with fewer than 10 randomized patients will be pooled for statistical analyses. Pooled country will be employed for all formal statistical model-based analyses as a block factor unless otherwise denoted.

Unless otherwise specified, all tests of treatment effects will be conducted at a 2-sided alpha level of 0.05, and confidence intervals (CIs) will be calculated at 95%, 2-sided. All tests of interactions between treatments and factors of interest will be conducted at a 2-sided alpha level of 0.10. Multiplicity adjustment will be performed among the hypotheses related to the primary and secondary efficacy endpoints.

The baseline visit will be Visit 3. For all variables, including HbA1c, if baseline data are not available or are missing, the last nonmissing measurement taken up to the first dosing date/time will be used for the baseline measurement. The efficacy measure for the primary analysis is defined as the change from baseline in HbA1c to Week 36 (Visit 9).

For all statistical analyses, missing data will be treated as missing at random for all analyses unless otherwise specified.

The treatment groups mentioned in this document are based on the randomized treatment groups: dulaglutide 4.5 mg, dulaglutide 3.0 mg, and dulaglutide 1.5 mg.

All efficacy and safety data will be summarized by each treatment group at each scheduled visit unless otherwise indicated. Dulaglutide 1.5 mg will serve as the reference treatment for treatment comparison in all efficacy analyses unless otherwise specified.

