Summary statistics for categorical measures will include number of subjects and percentages. The proportions of patients achieving target HbA1c $<7.0\%$ and $\leq 6.5\%$ at Week 36 (Visit 9) will be analyzed using a longitudinal logistic regression with repeated measurements. In this model, pooled country, treatment, visit, and treatment-by-visit interaction will be fit as fixed effects, and baseline HbA1c as a covariate. A logistic regression model will be applied for the aforementioned HbA1c target analysis at Week 36 (Visit 9) using LOCF by removing visit-related terms from the corresponding longitudinal logistic regression model.

For the analysis of other categorical measures, Fisher's exact test will be used for treatment comparisons unless otherwise specified. Categorical variables will be summarized by sample size and the number of patients and percentages for each treatment group at each visit. Imputed data may be applied in model-based data analyses, but will not be used in data listings. The latter will only present the non-imputed raw data, including site-reported scheduled and unscheduled visits, or early termination visit data; however, only scheduled visits for the measure of interest will be included in the summary table and statistical inference unless otherwise stated.

All statistical analyses will be conducted with SAS Version 9.4® or higher unless otherwise stated.

For primary DBL, all tables, figures, and listings (TFLs) will use the data up to Week 36 (Visit 9) or the study discontinuation date, whichever is earlier, unless otherwise specified.

For the final DBL delivery, TFLs will use the data up to the end of the treatment period (Week 52 [Visit 11]) or the study discontinuation date, whichever is earlier, unless otherwise stated.

Before each DBL, all key data will be reviewed. Any decision to exclude either subjects or observations from the statistical analyses will be made and documented by the study team, and will include the rationale.

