6.10.4. Clinical Laboratory Evaluation

Analyses of eGFR, creatinine, and UACR are described in Section 6.10.1.2.9. For other laboratory safety parameters, summaries will be provided in this section. For continuous (numeric) laboratory analytes, including serum lipid parameters (total cholesterol, high-density lipoprotein cholesterol, low-density lipoprotein cholesterol, very-low density lipoprotein cholesterol, and triglycerides), the rank of the change from baseline to endpoint (Week 36 [Visit 9] for primary DBL, Week 52 [Visit 11] for final DBL) will be analyzed as detailed in Section 6.1. For qualitative laboratory analytes, the numbers and percentages of patients with normal and abnormal values will be summarized by treatment.

Each pancreatic enzyme (pancreatic amylase [p-amylase] and lipase) and the maximum postbaseline value will be summarized by treatment in a shift table using $>1 \times \text{ULN}$ and $\geq 3 \times \text{ULN}$ separately for the Safety Population, Safety Population with normal baseline value, and Safety Population with baseline value $>1 \times \text{ULN}$.

An MMRM with pooled country, baseline HbA1c strata, treatment, visit, and treatment-by-visit interaction as fixed effects will be fit to analyze each pancreatic enzyme up to Week 52 (Visit 11). In this model, the log-transformed (post first dose measure/baseline measure) will be

the response variable, and log-transformed baseline measure will be used instead of baseline measure. The variance-covariance structure selection is detailed in Section 6.1.

An ANCOVA model for Week 36 (Visit 9) measurement using LOCF will be fit with the same model as the aforementioned MMRM but removing all terms containing visit.

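### The SAP tabulates the ECG limits for heart rate, PR interval and QTcF by visit only; no by-dose count of patients who cross a limit at any postbaseline ECG is pre-specified.

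*SAP*

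**What the plan says.** SAP 6.10.2 fixes both the parameters and the layout of the numeric ECG analysis: "The threshold analyses will only include HR, PR interval, and QTcF, by visit and treatment". The word 'only' restricts the parameters; the by-visit layout comes from the end of the sentence. Protocol 10.3.4.7 is consistent with this: descriptive statistics for ECG parameters, including clinically relevant changes, "will be presented by treatment and visit. These parameters will be analyzed using a similar MMRM".

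The general rules in SAP 6.1 point the same way. "All efficacy and safety data will be summarized by each treatment group at each scheduled visit unless otherwise indicated", and "Categorical variables will be summarized by sample size and the number of patients and percentages for each treatment group at each visit". For categorical measures not otherwise covered, Fisher's "exact test will be used for treatment comparisons unless otherwise specified". SAP 6.1 places unscheduled and early-termination data in listings and then says that "only scheduled visits for the measure of interest will be included in the summary table and statistical inference unless otherwise stated".

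Elsewhere the SAP works per patient on the worst value. In SAP 6.10.4, for each pancreatic enzyme, "the maximum postbaseline value will be summarized by treatment in a shift table". SAP 6.10.1.2.9 uses minimum eGFR and maximum creatinine and UACR, and the SAP 6.10.4 shift tables, including liver tests, use the maximum postbaseline value.

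"Electrocardiogram (ECG) parameters" are listed in SAP Table GBGL.1 among the secondary safety endpoints, with each higher dose to be compared with 1.5 mg.

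**The concern.** Table GBGL.3 exists to find patients in the tail: QTcF above 500 msec or up by more than 60 msec, PR of 220 msec or more, heart rate above 100 with a rise above 15 bpm. The natural safety question is how many patients in each arm ever got there. A by-visit layout does not answer it. If crossings come and go, each table shows only some of the affected patients, in small numbers.

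Heart rate has a history in this programme. Protocol 3.2 records that heart rate increases were among the reasons the monitoring committee of the earlier dose-finding study recommended stopping 3.0 mg. This trial tests that dose and a higher one.

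The exclusion of early-termination and unscheduled ECGs adds to the problem. The Schedule of Activities collects an ECG at early termination, and protocol 9.2.2.6 calls for one when an arrhythmia or conduction event occurs. A crossing is plausible on either occasion.

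**Working it through.** **What the plan gives.** No crossing rate, within-patient correlation or power is stated for the ECG limits, so there is no ECG figure to reproduce. The only power statement concerns HbA1c (SAP 5.2: at least 80%), and it holds. With 510 per arm, difference 0.22 and SD 1.1, power is Φ(0.22/1.1 × √(510/2) − z). This is 89% at two-sided 0.05 (z = 1.96) and 83% at 0.025 (z = 2.24).

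**ECG visits.** The Schedule of Activities places treatment-period ECGs at Visits 6, 7, 9 and 11 (Weeks 12, 18, 36 and 52). Under protocol Table GBGL.2 the 4.5 mg arm reaches its final dose from Week 13, so Weeks 18, 36 and 52 are the ECG visits with all arms on final dose. Outputs at the primary lock stop at Week 36 (SAP 6.1).

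**Why visit tables cannot be added.** If 10 patients in an arm cross at each of three visits, the number who ever cross lies anywhere from 10 (the same patients each time) to 30 (all different).

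**Illustration.** Assumptions: 540 patients per arm with all ECGs (between the documents' 510 and 600); per-visit rate p on 1.5 mg and 2p on a higher dose; Fisher's exact test, two-sided 0.05. A patient's ECG values at k visits are modelled as equicorrelated normal variables with correlation ρ and cut-off c = Φ⁻¹(1 − p). Then

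P(ever crosses) = 1 − ∫ φ(u) [Φ((c − √ρ·u)/√(1 − ρ))]^k du.

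Fisher power is by exact enumeration.

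| Per-visit rates | Power, one visit | k = 3: ever-crossed rates, ρ = 0.6 / 0.3 | k = 3: power, ρ = 0.6 / 0.3 | k = 3: power, ρ = 0.9 |
|---|---|---|---|---|
| 1% vs 2% | 19% | 2.5% vs 4.8% / 2.8% vs 5.5% | 47% / 55% | 33% |
| 2% vs 4% | 43% | 4.8% vs 9.1% / 5.5% vs 10.6% | 76% / 85% | 60% |

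As counts, 2% versus 4% is about 11 versus 22 patients at one visit (540 × 0.02 = 10.8; 540 × 0.04 = 21.6). Ever crossed, it is about 26 versus 49 (ρ = 0.6) or 30 versus 57 (ρ = 0.3). With Weeks 18 and 36 only (k = 2), 2% versus 4% gives 65-71% at ρ = 0.6 to 0.3.

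**Share of power lost at one visit.** For 1% versus 2%: 1 − 19.4/46.7 = 58% to 1 − 19.4/55.1 = 65%. For 2% versus 4%: 1 − 42.7/76.3 = 44% to 1 − 42.7/84.7 = 50% (49.6% before rounding).

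**Higher rates.** A normal-approximation run with 600 per arm, four visits and correlation 0.9 down to 0 gives 71% at one visit versus 87% to over 99% for 3% versus 6%, and 91% versus 98% to over 99% for 5% versus 10%.

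**Reading all visit tests together.** A Fisher simulation with 600 per arm and four visits, 1% versus 2%, finds at least one significant visit in 63%, 57% and 51% of runs at correlation 0, 0.5 and 0.8. The single ever-crossed test gives 78%, 64% and 49%. The chance of a false signal from four tests is about 9% at a 1% rate and 10-15% at 2% to 5%.

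**The case against.** A reader might infer that patients crossing ECG limits are never compared by dose. The documents do not support that. Fisher's exact test applies by default at each visit, and SAP 6.10.2 also plans an MMRM on change in heart rate, PR and QTcF. Qualitative conduction and rhythm abnormalities are reported by treatment, arrhythmia and conduction events are summarised by treatment (SAP 6.10.1.2.7), and exposure-response work on QT, PR and heart rate is planned (protocol 10.3.5).

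The MMRM is the strongest answer. In the latent model used above, a doubling from 1% to 2% is a mean shift of 2.326 − 2.054 = 0.27 SD, and from 2% to 4% it is 2.054 − 1.751 = 0.30 SD. A simple two-sample comparison at one visit with 540 per arm, Φ(shift × √(540/2) − 1.96), detects either with at least 99% power. This stands for a general shift. It does not cover a small group of outliers, which is what a threshold table is for.

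A reader might also infer that most of the power is lost. That is no figure from the documents, and it fails at 2% and above in the three-visit illustration, when crossings persist strongly between visits, or when all visit tests are read together. At correlation 0.8 in the simulation the ever-crossed test has no advantage over scanning the four visits (49% versus 51%), although scanning inflates false signals and the SAP gives no rule for reading it.

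Finally, SAP 6.1 allows additional analyses without amendment. That is true, but a count chosen after unblinding carries less weight than one fixed beforehand.

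**Conclusion.** The gap is real and limited. The numeric ECG limits are planned by visit only, the patient-level any-visit count by dose is not pre-specified, and on the plain reading of SAP 6.1 crossings found only at early-termination or unscheduled ECGs reach the listings but no threshold table. None of the other planned ECG analyses supplies that count.

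The size depends on inputs the documents do not give. For rare, intermittent crossings (about 1% per visit), the any-visit count raises power for a doubling from about 19% to 47-55%; at 2% per visit, from 43% to 76-85%. At 5% per visit, or with strong persistence, the gain is small. That crossings are intermittent is itself an assumption. No planned analysis is invalid and no alpha-controlled conclusion is touched. This is a low-cost improvement to a secondary safety endpoint, and it would bring the ECG limits into line with the SAP's own handling of pancreatic, renal and liver measures.

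**What to change.** In SAP 6.10.2 add, by arm, the number and percentage of patients meeting each postbaseline criterion of Table GBGL.3 at any postbaseline ECG:

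- through Week 36, through Week 52, and from Week 18 onward, when all arms are on final dose;
- including early-termination and unscheduled ECGs, as a stated exception to the scheduled-visit rule in SAP 6.1;
- for the limits with no change-from-baseline condition (PR 220 msec or more; QTcF above 450 in men or 470 in women, above 480, above 500), among patients below that limit at baseline, so that pre-existing abnormality is not counted as new;
- with risk differences and 95% CIs for each higher dose versus 1.5 mg.

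Keep the by-visit tables as supportive. State the same any-visit rule for the vital-sign limits in Table GBGL.4. SAP 6.10.3 does not itself say by visit and leaves that layout to the general default.

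The cost is a few extra rows from data already collected. The one drawback is that an any-visit count depends mildly on how many ECGs a patient has, and unscheduled ECGs follow symptoms. Report ECGs per patient by arm, and show the result with and without unscheduled ECGs.

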6.10.3. Vital Signs

Vital signs will be summarized for the Safety Population. Prior to any analyses, the arithmetic mean from the triplicates for the same parameter collected at the same visit taken from the same patient will be calculated and used for all subsequent analyses. The changes from baseline in pulse rate, systolic blood pressure (SBP), diastolic blood pressure (DBP), and rate pressure product (RPP [$\text{SBP} \times \text{pulse rate} / 1000$]) will be analyzed using an MMRM similar to that described in Section 6.1. The threshold analyses will be summarized with the threshold definitions listed in Table GBGL.4.

Table GBGL.4. Abnormality Criteria for Pulse Rate, Systolic Blood Pressure, and Diastolic Blood Pressure

Parameter (Unit)	Visit	Threshold Definition
Pulse rate (bpm)	Baseline (Visit 3)	$>100, \geq 130$
	Postbaseline	>100 and $\text{CFB} > 15$
SBP (mm Hg)	Baseline (Visit 3)	$\geq 160, \leq 90$
	Postbaseline	≥ 160 and $\text{CFB} \geq 20$
		≤ 90 and $\text{CFB} \leq -20$
DBP (mm Hg)	Baseline (Visit 3)	$\geq 100, \leq 50$
	Postbaseline	≥ 100 and $\text{CFB} \geq 10$
		≤ 50 and $\text{CFB} \leq -10$

Abbreviations: CFB = change from baseline; DBP = diastolic blood pressure; SBP = systolic blood pressure.

6.10.4. Clinical Laboratory Evaluation

Analyses of eGFR, creatinine, and UACR are described in Section 6.10.1.2.9. For other laboratory safety parameters, summaries will be provided in this section. For continuous (numeric) laboratory analytes, including serum lipid parameters (total cholesterol, high-density lipoprotein cholesterol, low-density lipoprotein cholesterol, very-low density lipoprotein cholesterol, and triglycerides), the rank of the change from baseline to endpoint (Week 36 [Visit 9] for primary DBL, Week 52 [Visit 11] for final DBL) will be analyzed as detailed in Section 6.1. For qualitative laboratory analytes, the numbers and percentages of patients with normal and abnormal values will be summarized by treatment.

Each pancreatic enzyme (pancreatic amylase [p-amylase] and lipase) and the maximum postbaseline value will be summarized by treatment in a shift table using $>1 \times \text{ULN}$ and $\geq 3 \times \text{ULN}$ separately for the Safety Population, Safety Population with normal baseline value, and Safety Population with baseline value $>1 \times \text{ULN}$.

An MMRM with pooled country, baseline HbA1c strata, treatment, visit, and treatment-by-visit interaction as fixed effects will be fit to analyze each pancreatic enzyme up to Week 52 (Visit 11). In this model, the log-transformed (post first dose measure/baseline measure) will be

the response variable, and log-transformed baseline measure will be used instead of baseline measure. The variance-covariance structure selection is detailed in Section 6.1.

An ANCOVA model for Week 36 (Visit 9) measurement using LOCF will be fit with the same model as the aforementioned MMRM but removing all terms containing visit.

A summary report and analysis for treatment-emergent abnormal laboratory values (outside the reference ranges as appropriate) will be provided for each continuous analyte by treatment. Shift tables of the change from baseline value to the maximum postbaseline value to endpoint for selected analytes using clinically meaningful thresholds will be summarized descriptively. A shift table for alanine aminotransferase, aspartate aminotransferase, alkaline phosphatase, total bilirubin level, and direct bilirubin will be generated using the following cutoffs: $\leq 1 \times \text{ULN}$, ($> 1 \times \text{ULN}$ and $< 3 \times \text{ULN}$), ($\geq 3 \times \text{ULN}$ and $< 5 \times \text{ULN}$), ($\geq 5 \times \text{ULN}$ and $< 8 \times \text{ULN}$), and $\geq 8 \times \text{ULN}$.

